### **Sensitivity Analyses**

A sensitivity analysis will be done on the primary endpoint, repeating the primary analysis using the PPS which excludes those with protocol deviations that are judged to have a potential impact

on the analysis of the primary endpoint. This sensitivity analysis is expected to be sufficient to evaluate the supportive estimand discussed in Section 3.1.1.2.

As outlined in Section 7.1.1.1 the primary endpoint will be derived conditional on there being scores available on at least 4 of the 7 days over which the average will be calculated. To evaluate the potential impact of this rule for dealing with missing data in deriving the average score an additional analysis will be run which includes the weekly average, where the weekly average is derived regardless of the number of days data available within that week. That is, it will include a weekly average calculated for weeks in which there is at least one NRS score recorded. Depending on the level of missing data further derivations of the weekly average may be examined post-hoc.

### 7.1.2 Secondary Efficacy Endpoints

### 7.1.2.1 IPF Coughing Severity Scale

The mean change from baseline to Week 2 in weekly average of the daily IPF Coughing Severity Scale will be assessed. An ANCOVA model, similar to that suggested for the primary endpoint, will be used to assess this endpoint at Week 2. Least square means and corresponding 95% CIs will be presented by treatment group/cohort. Mean differences, corresponding CIs and p-values for treatment comparisons between orvepitant (10 mg or 30 mg once daily) and placebo will also be presented. Derivation of weekly averages will use the same rules as for the primary endpoint.

### 7.1.2.2 Early Morning Coughing Scale

The mean change from baseline to Weeks 2 and 4 in weekly average of the daily early morning coughing scale will be assessed. An ANCOVA model, similar to that suggested for the primary endpoint, will be used to assess this endpoint separately by time point (Week 2 or Week 4). Least square means and corresponding 95% CIs will be presented at Week 2 and Week 4 by treatment group/cohort. Mean differences, corresponding CIs and p-values for treatment comparisons between orvepitant (10 mg or 30 mg once daily) and placebo will also be presented. Derivation of weekly averages will use the same rules as for the primary endpoint.

### 7.1.2.3 Rest of The Day Coughing Scale

The mean change from baseline to Weeks 2 and 4 in weekly average of the daily rest of the day coughing scale will be assessed. An ANCOVA model, similar to that suggested for the primary endpoint, will be used to assess this endpoint separately by time point (Week 2 or Week 4). Least square means and corresponding 95% CIs will be presented at Week 2 and Week 4 by treatment group/cohort. Mean differences, corresponding CIs and p-values for treatment comparisons between orvepitant (10 mg or 30 mg once daily) and placebo will also be presented. Derivation of weekly averages will use the same rules as for the primary endpoint.

### 7.1.2.4 Urge To Cough Scale

The mean change from baseline to Weeks 2 and 4 in weekly average of the daily urge to cough scale will be assessed. An ANCOVA model, similar to that suggested for the primary endpoint, will be used to assess this endpoint separately by time point (Week 2 or Week 4). Least square means and corresponding 95% CIs will be presented at Week 2 and Week 4 by treatment group/cohort. Mean differences, corresponding CIs and p-values for treatment comparisons

Page 29 of 50

between orvepitant (10 mg or 30 mg once daily) and placebo will also be presented. Derivation of weekly averages will use the same rules as for the primary endpoint.

### 7.1.2.5 Dyspnoea Scale

The mean change from baseline to Weeks 2 and 4 in weekly average of the daily dyspnoea scale will be assessed. An ANCOVA model, similar to that suggested for the primary endpoint, will be used to assess this endpoint separately by time point (Week 2 or Week 4). Least square means and corresponding 95% CIs will be presented at Week 2 and Week 4 by treatment group/cohort. Mean differences, corresponding CIs and p-values for treatment comparisons between orvepitant (10 mg or 30 mg once daily) and placebo will also be presented. Derivation of weekly averages will use the same rules as for the primary endpoint.

### 7.1.2.6 Cough Frequency Scale

The mean change from baseline to Weeks 2 and 4 in weekly average of the daily cough frequency scale will be assessed. An ANCOVA model, similar to that suggested for the primary endpoint, will be used to assess this endpoint separately by time point (Week 2 or Week 4) and cohort. Least square means and corresponding 95% CIs will be presented at Week 2 and Week 4 by treatment group/cohort. Mean differences, corresponding CIs and p-values for treatment comparison between orvepitant (10 mg or 30 mg once daily) and placebo will also be presented. For these analyses, the daily verbal rating scale scores will be converted to a numerical values (where Never = 0 and All the time = 4) and derivation of weekly averages will use the same rules as for the primary endpoint.

In addition, a summary for the cough frequency scale will be presented of the modal response during the 7 days prior and up to each assessment time point. Frequency tables will display the frequency and percentage of subjects in each category at Weeks 2 and 4. Shift from baseline tables will also be provided at Weeks 2 and 4 with baseline category as columns and Week 2 (or Week 4) category as rows.

### 7.1.2.7 Patient Global Rating of Status

Patient global ratings of status for all coughing, early morning coughing and rest of the day coughing will be summarised with frequency tables by displaying the frequency and percentage of subjects in each category at Weeks 2 and 4. Shift from baseline tables will also be provided at Weeks 2 and 4 with baseline category as columns and Week 2 (or Week 4) category as rows.

### 7.1.2.8 Patient Global Rating of Change

Patient global ratings of change for all coughing, early morning coughing and rest of the day coughing will be summarised in the same way as the patient global rating of status with frequency tables for each category at weeks 2 and 4. Shift from baseline summaries will be not applicable as there is no baseline recorded for this endpoint.

Additionally, the patient global rating of change analysis will combine the numerical levels into the following groups for each question in the patient global rating analysis:

- Improved Global Rating of Change: Scores 1, 2, 3
- No Change: Score 0

• Worsened: Scores -3, -2, -1

For each question, frequency tables will be provided for each of the combined categories above at weeks 2 and 4.

### 7.1.2.9 Leicester Cough Questionnaire

The LCQ is a 19-item questionnaire that assesses cough-related Quality-of-Life. It has three domains (physical, psychological and social). The total score range is 3-21 and domain scores each range from 1-7; a higher score indicates a better Quality-of-Life.

The analysis of change from baseline in LCQ total score and the three domain scores will be analysed in the same way as for the primary endpoint. That is, an ANCOVA model will be used to assess change from baseline in LCQ total score and separately for each domain from baseline to Week 4.

The Domains are comprised of the following questions:

a) Physical: 1,2,3,9,10,11,14,15

b) Psychological: 4,5,6,12,13,16,17

c) Social: 7,8,18,19

The individual domain scores are calculated by dividing the total score from items in the domain by the number of items in the domain.

1) Total scores: addition of domain scores (range 3-21).

The 10% rule, as recommended by the originator of the assessment, will be used for missing data as follows:

- Physical domain: only 1 missing item allowed. (2 missing items = cannot calculate score)
- Psychological domain: only 1 missing item allowed.
- Social domain: no missing items allowed.
- Total score: always requires all 3 domain scores.

The average score for items available for a specific domain is used as the value for the missing item.

### 7.1.2.10 Cough Frequency

Cough frequency is measured using the Leicester Cough Monitor ambulatory cough monitor applied for 24-hours at the Baseline visit (Period A) and in Week 4 of each treatment period.

Cough frequency data will be log transformed before modelling (descriptive summaries will still be performed using the original values). If there are subjects with cough frequencies of 0, 1 will be added prior to log transformation and will then be subtracted from the back-transformed value. Data will be tested for normality prior to transformation. An ANCOVA model similar to the primary endpoint will be used except only baseline for Period A will be used as there is no baseline available for Period B. The following will be assessed for Mean change from baseline to Week 4:

Page 31 of 50

Statistical Analysis Plan Final V1.0, 14 Mar 2024

NeRRe Therapeutics Ltd Protocol: ORV-PF-01

- Average number of coughs per hour in the 24 hour period
- Average number of coughs per hour in the awake period
- Average number of coughs per hour in the asleep period
- Average number of bouts per hour in the 24 hour period
- Average number of bouts per hour in the awake period
- Average number of bouts per hour in the asleep period
- Average number of coughs in a cough bout in the 24 hour period
- Average number of coughs in a cough bout in the awake period
- Average number of coughs in a cough bout in the asleep period.

The treatment effect will be estimated using the ratio of geometric means (i.e. the difference between the treatments least squares means [adjusted means] on the log scale, back-transformed to the original scale). The ratio of GM ratios is the geometric mean ratio (orvepitant [10 mg or 30 mg once daily]/ Placebo) of the Week 4/baseline result. The adjusted geometric mean (GM) ratio (Week 4/baseline) and corresponding 95% CIs for each treatment group, ratio of GM ratios (orvepitant [10 mg or 30 mg once daily]/Placebo), 95% CIs for the ratio of GM ratios and the p-value from the hypothesis test of no difference between the treatment groups at Week 4 will be presented by cohort.

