### 3.2 SECONDARY EFFICACY ENDPOINTS

The secondary efficacy endpoints comprise the following:

Assessment	Secondary Efficacy Endpoints
IPF coughing severity scale	Mean change from baseline to Week 2 in weekly average of the daily IPF coughing severity scale
Early morning coughing scale	Mean change from baseline to Weeks 2 and 4 in weekly average of the daily early morning coughing scale
Rest of the day coughing scale	Mean change from baseline to Weeks 2 and 4 in weekly average of the daily rest of the day coughing scale
Urge to cough scale	Mean change from baseline to Weeks 2 and 4 in weekly average of the daily urge to cough scale
Dyspnoea scale	Mean change from baseline to Weeks 2 and 4 in weekly average of the daily dyspnoea scale
Cough frequency scale	Mean change from baseline to Weeks 2 and 4 in weekly average of the daily cough frequency scale
Patient global ratings of status for all coughing, early morning	Proportion of subjects in each category at Weeks 2 and 4

coughing and rest of the day	
Patient global ratings of change for all coughing, early morning coughing and rest of the day	Proportion of subjects in each category at Weeks 2 and 4
coughing  Cough frequency measured using the Leicester Cough  Monitor ambulatory cough monitor	
 
Mean change from baseline to Week 4 in 24-hour cough frequency
 
Mean change from baseline to Week 4 in awake cough frequency
 

	Mean change from baseline to Week 4 in night-time cough frequency
	Mean change from baseline to Week 4 in the number of coughing bouts
Leicester Cough Questionnaire (LCQ)	Mean change from baseline to Week 4 in LCQ total and domain (Physical, Social, Psychological) scores
King's Brief Interstitial Lung Disease health status questionnaire (K-BILD)	Mean change from baseline to Week 4 in K-BILD total and domain (Psychological, Breathlessness and Chest Symptoms) scores
	Proportion of patients with a clinically relevant improvement in total K-BILD score
PROMIS SF SD 8b sleep assessment questionnaire	Mean change from baseline to Week 4 in the PROMIS SF SD 8b score
Hospital Anxiety and Depression Scale (HADS) questionnaire	Mean change from baseline to Week 4 in the HADS score
Hull Airway Reflux Questionnaire (HARQ)	Mean change from baseline to Week 4 in HARQ score

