### 5 GENERAL ASPECTS FOR STATISTICAL ANALYSES

### 5.1 GENERAL METHODS

- All analyses and summaries will be produced using SAS® version 9.4 (or higher).
- All analysis will be analysed by cohort such that there will be two placebo groups presented unless specified otherwise.
- Categorical variables will be summarised using the number of observations (n), frequency and
  percentage of subjects. All percentages will be presented as one-decimal point, unless
  otherwise specified. Percentages equal to 100 will be presented as 100% and percentages will
  not be presented for zero frequencies.
- If log transformation is to be applied prior to analysis, a positive constant (1) will be added in cases of zero value prior to transformation. Analysis results will be back transformed to the original scale for reporting.
- Continuous variables and ordered categorical data will be summarised using the number of subjects with evaluable data, mean, standard deviation (SD), geometric mean (where

Page 21 of 50

Statistical Analysis Plan Final V1.0, 14 Mar 2024

NeRRe Therapeutics Ltd Protocol: ORV-PF-01

appropriate), median, first and third quartiles, minimum and maximum. In case of 0 values where geometric mean is calculated, 1 is added to every number in the data set, and then subtracted from the resulting geometric mean. The same number of decimal places as in the raw data will be presented when reporting minimum and maximum, 1 more decimal place than in the raw data will be presented when reporting the mean and median, and 2 more decimal places than in the raw data will be presented when reporting the SD. For ordered categorical data and nominal data, absolute counts and relative frequencies (in %) will be calculated.

- Lower and upper bound values for the confidence intervals (CIs) will be reported to 2 more decimal places than the raw data.
- All statistical hypothesis tests and CIs will be two sided, using a type I error rate of 0.05.
- Unless stated otherwise, the percentages will be based on the number of non-missing observations. The column header will still contain the number of subjects in the treatment group. There will be a row for the number of non-missing observations in the table (at each time point, if required) for each variable being summarised.
- Any calculated p-values will be presented to 3 decimal places; p-values less than 0.001 will be presented as 'p<0.001' and p-values greater than 0.999 will be presented as 'p>0.999'.

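### If a cough-frequency value is 0, SAP 7.1.2.10 as written subtracts 1 from back-transformed results that are all ratios, which does not undo the offset

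*SAP*

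**What the plan says.** SAP 7.1.2.10 log-transforms cough frequency before fitting an ANCOVA like that of the primary endpoint. If any subject has a frequency of 0, "1 will be added prior to log transformation and will then be subtracted from the back-transformed value". The section then lists the model results to be presented: "The adjusted geometric mean (GM) ratio (Week 4/baseline) and corresponding 95% CIs for each treatment group, ratio of GM ratios" (orvepitant over placebo), the interval for that second ratio, and a p-value. It lists no adjusted geometric mean on the coughs-per-hour scale. Outside the model, "descriptive summaries will still be performed using the original values".

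The outcomes analysed this way include "Average number of coughs per hour in the asleep period". SAP 3.2 names the corresponding secondary endpoint: "Mean change from baseline to Week 4 in night-time cough frequency".

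SAP 5.1 has two general rules on zeros:
- For logs, "a positive constant (1) will be added in cases of zero value prior to transformation", followed by "Analysis results will be back transformed to the original scale for reporting". No subtraction is mentioned.
- For descriptive geometric means, "1 is added to every number in the data set, and then subtracted from the resulting geometric mean".

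**The concern.** Adding 1 before the log and subtracting 1 afterwards is a coherent pair of steps for a single geometric mean, and SAP 5.1 uses it that way. Section 7.1.2.10 applies the same pair where nothing but ratios is back-transformed. Followed literally, the rule prints negative numbers in columns labelled as geometric mean ratios and moves the no-effect value from 1 to 0. A reader who compared such an interval with 1 would draw the wrong conclusion.

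A smaller wording matter sits beside this. The two 5.1 rules describe the reach of the added constant differently: one speaks of cases of zero, the other of every number. Unlike the subtraction, the reach of the constant cannot be seen in a finished table, and it can move both the estimate and the p-value.

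**Working it through.** The plan gives no figure of its own to reproduce here, so the check follows the rule through the outputs.

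**Subtraction.** Let Y0 be the baseline rate and Y4 the Week 4 rate, with 1 added to each. For a single geometric mean, exp(mean of log(Y + 1)) - 1 returns to the original scale. For the planned outputs, leaving covariate adjustment aside:
- per treatment: exp(mean of [log(Y4 + 1) - log(Y0 + 1)]) = GM(Y4 + 1) / GM(Y0 + 1)
- between treatments: the ratio of two such ratios.

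Subtracting 1 from the first gives [GM(Y4 + 1) - GM(Y0 + 1)] / GM(Y0 + 1). That is a proportional change in (rate + 1), not a ratio of rates. In numbers:
- 0.54 - 1 = -0.46. The 0.54 is the Week 12 geometric mean ratio to baseline for awake cough on 30 mg, in the earlier study described in Protocol 5.6. It is used only as a familiar number. The median awake rate there was 32 coughs per hour, so zeros would not be expected.
- 1.00 - 1 = 0.
- An assumed ratio of 0.75 with interval 0.55 to 1.02 becomes -0.25 with interval -0.45 to 0.02.

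The test is done on the log scale, so the p-value does not change.

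**Which values receive the 1.** Take one subject who falls from 0.5 per hour to 0:
- zeros only: 1 / 0.5 = 2.0, an apparent doubling
- every value: (0 + 1) / (0.5 + 1) = 0.67, a fall.

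Adding 1 to every value has its own cost. A true halving from x reads as (x/2 + 1) / (x + 1), which is 0.75 at x = 1, 0.67 at x = 2 and 0.515 at x = 32.

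**Illustrative simulation.** Only the 37 subjects per cohort comes from the documents. The assumptions are 7 hours asleep, Poisson counts, log-scale SDs of 1.0 between and 0.6 within subjects, and a period-adjusted paired log difference. There were 4,000 cohorts per setting, and results are for cohorts with at least one zero. For a true ratio of 0.50:

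| Placebo median, per hour | Share of zeros | Power: every value / zeros only | Median estimate: every value / zeros only |
|---|---|---|---|
| 0.5 | 20% | 0.91 / 0.30 | 0.81 / 0.77 |
| 1 | 10% | 0.96 / 0.74 | 0.74 / 0.62 |
| 2 | 4% | 0.98 / 0.94 | 0.68 / 0.55 |
| 5 | 2% | 0.99 / 0.99 | 0.60 / 0.51 |

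At 5 per hour only about 46% of cohorts contain any zero, and zeros are 0.9% of values over all cohorts.

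The share of these cohorts in which the two readings fall on opposite sides of p = 0.05 depends on the true ratio:
- at 0.5 per hour: about 62% for a ratio of 0.50, 25% for 0.75 and 8% for no effect
- at 5 per hour: about 1%, 13 to 15% (repeated runs differ) and 2%.

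With no effect, each reading rejects in about 4 to 6% of cohorts.

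**The case against.** The strongest reply is that this is a drafting slip that could not survive the first table. A negative ratio is plainly impossible, the shift is reversed by adding 1 back, and inference is untouched. SAP 13.1 and 13.2 also provide for output specifications, their review, and independent double programming. All of that stands and is why the point is minor. It does not make the sentence correct. Double programming compares code with the specification, and here the specification contains the error. It is true that a ratio minus 1 can be read as a proportional change, but the section labels these outputs ratios.

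A reader might infer something stronger: that the SAP leaves the reach of the constant open, so the night-time p-values are not pre-specified. The documents do not support that. Section 7.1.2.10 is the specific rule. It does not limit the addition to the zero values, and subtracting a common constant afterwards makes sense only if it was added throughout. The geometric-mean rule in 5.1 says so outright for the same operation. Only the looser phrase in the 5.1 log bullet points towards zeros only. Nor can the simulated disagreement be quoted as the size of a problem in this trial, because the documents give neither an asleep cough rate nor a rate of zeros.

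**Conclusion.** The subtraction is wrong as written for every back-transformed result listed in 7.1.2.10, and this follows from the text and algebra alone. It takes effect only if a zero is recorded. The asleep-period outcomes are the most plausible place for that, which is a judgement and not a figure in the documents. Only secondary endpoints are involved; the primary endpoint is unaffected. Severity is minor.

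The reach of the added constant is a wording clarification, not a second error. Adding 1 to every value is both the better reading of 7.1.2.10 and the better choice, because it preserves the order of values and, in the settings simulated with a true halving, has equal or better power. It is not free of distortion: under those assumptions it pulls the ratio towards 1 by more, on average, than zeros-only does.

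**What to change.** - In SAP 7.1.2.10, remove the subtraction for the geometric mean ratios, the ratio of those ratios, and all their confidence intervals. Keep it only for a single geometric mean, consistent with 5.1.
- In the log bullet of 5.1 and in 7.1.2.10, state that when a zero occurs in an endpoint, 1 is added to every observation of that endpoint in the analysis: baseline and Week 4, both treatments.
- Label the affected result a ratio of (rate + 1), with a note that it lies closer to 1 than the ratio of rates when rates are low.

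The cost is two or three sentences and one table label, with no new data and no change to the model. It should be settled before unblinding.

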## 7.1.2.11 King's Brief Interstitial Lung Disease Questionnaire

The K-BILD is a brief, validated, self-completed health status measure for interstitial lung diseases. It comprises 15 questions in three domains. Domain scores are calculated as logit-transformed weighted sums of individual items within each domain. Domains are Psychological (items 3, 5, 6, 8, 10, 12, 14), Breathlessness (1, 4, 11, 13) and Chest Symptoms (2, 7, 9). (Note that item 15 does not belong to any of the domains and only contributes to the total score.) Domain scores are not calculated if 50% or more of the individual items for that domain are missing. Total score is calculated as the logit-transformed weighted sum of all items. Total score is not calculated if any of the three domain scores is missing. K-BILD will be completed by subjects at Visits 2, 4, 5 and 7.

If an item is missing, the patient's average score for items available for a specific domain is used as the value for the missing item (but only if most items in domain are available).

The average score for items available for a specific domain is used as the value for the missing item (but only if >50% items in domain are available).

Mean change from baseline to week 4 in total and domain scores will be analysed with an ANCOVA model similar to that used for the primary endpoint.

Page 32 of 50

Additionally, the proportion of patients with a clinically relevant improvement in K-BILD total score and 95% Clopper–Pearson CIs will be presented at week 4. Fisher's Exact Test will be used for computing p-value for treatment comparison between orvepitant (10 mg or 30 mg once daily) and placebo if computationally feasible (otherwise, the Chi-Square Test may be used if the expected count in any cell is greater than 5).

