### 2.4 TRIAL DESCRIPTION

The study will be a multi-center, double-blind, randomised, placebo-controlled 2-period crossover design. Two doses of orvepitant, 10 and 30 mg once daily, will be evaluated.

Subjects will participate in one of two cohorts (Cohort 1 [30 mg] and Cohort 2 [10 mg]). Within each cohort, subjects will be randomised to receive either orvepitant or placebo in the first treatment period (Treatment Period A) followed by the alternate treatment in Treatment Period B. There will be a wash-out period of 3 weeks between the two treatment periods. Subjects will be randomised 1:1 to each of the two treatment orders and 1:1 to each cohort.

Subjects will enter a screening period of up to 28 days to determine eligibility. Eligible subjects will be randomised at the Baseline visit and will participate in two identical 4-week treatment periods with the wash-out period between them. There will be a total of 8 visits including the Screening, Baseline and final Follow-up visits (Table 2 of the protocol).

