### **5.2.2** Baseline Values

Baseline values will be defined separately for each treatment period, unless stated otherwise.

For the primary efficacy endpoint (mean change from baseline to Week 4 in weekly average of the daily IPF Coughing Severity Scale score), period-specific baseline will be used in the analysis, which is the average of the 7 calendar days up to and including the date of Visit 2 for Treatment Period A and the average of 7 calendar days up to and including the date Visit 5 for Treatment Period B.

For secondary efficacy endpoints related to change from baseline, the period-specific baseline will be used when available; for those endpoints for which a period-specific baseline is not available

(cough frequency and Hull Airway Reflux Questionnaire), the baseline in Treatment Period A will be used.

For safety assessments, baseline will be Visit 2 for Treatment Period A and for Treatment Period B it will be Visit 5.

For both safety and efficacy assessments, if the period-specific baseline is missing for Treatment Period A the value from Visit 1 will be used. If this is missing change from baseline will not be calculated. If the period-specific baseline is missing for Treatment Period B the value from Visit 2 (first preference) or visit 1 (second preference) will be used. If both are missing change from baseline will not be calculated.

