### 7.1 PRIMARY AND SECONDARY EFFICACY ANALYSIS

Efficacy endpoints will be summarised separately for each cohort by descriptive statistics or counts and percentages for each treatment group at each time point, as appropriate. All statistical hypothesis tests and confidence intervals will be two sided, using a type I error rate of 0.05. No adjustments for multiple comparisons will be used.

The change from baseline of parameters in Week 4 (and Week 2 where also relevant) will be summarised for each treatment group in the FAS population.

Statistical comparisons for the primary and secondary endpoints will be done separately for each cohort as described below in each subsection. For the primary endpoint and secondary endpoints that are a daily numerical or verbal rating scale, an analysis of covariance (ANCOVA) model will be used with the response variable as the change from baseline in the mean score at the timepoint of interest, and predictor variables (fixed effects) as treatment, baseline mean score for the endpoint, period and interaction effect between treatment and period. Subject will be included as a random effect. Investigation of other covariates such as age and sex and their impact on the results may be done post-hoc. Sample SAS code for the ANCOVA is provided below.

Normality of error terms may be checked with QQ plots or other methods. If normality assumptions are considered severely violated, log transformation will be attempted first to see if that fixes the issue. If the normality assumption is still violated after applying transformation, a non-parametric method (e.g., Wilcoxon signed-rank test) will be used for conducting treatment comparison between orvepitant (10 mg or 30 mg once daily) and placebo.

All efficacy data, both patient-reported scores/assessments and derived parameters, will be listed.

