### 7.1.3 Sub-Groups

The primary efficacy endpoint will also be summarised descriptively by the following subgroups, provided there are a minimum of 10 evaluable subjects in each sub-group within the category and cohort:

 Total score increase of ≥5.0 ( et al. Sinha A, Patel AS, Siegert RJ, et alThe King's Brief Interstitial Lung Disease (KBILD) questionnaire: an updated minimal clinically important difference BMJ Open Respiratory Research 2019;6:e000363. doi: 10.1136/bmjresp-2018-000363)

Page 33 of 50

Category	Sub-group
Use of concomitant disease modifying therapies	Yes (using)
(nintedanib or pirfenidone) at baseline	No (not using)
IPF Cough Severity Scale score at baseline	≤ Median
	> Median
Sex	Male
	Female
Race	White
	Non-white
Ethnicity	Hispanic
	Non-hispanic

The awake cough frequency endpoint will also be summarised descriptively in the following sub-group:

By awake cough frequency at baseline (<=Median, >Median)

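### The K-BILD responder comparison uses Fisher's exact test for independent groups, although the same crossover patients supply both sides

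*SAP*

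**What the plan says.** SAP 7.1.2.11 presents the proportion of patients with a clinically relevant improvement in K-BILD total score at Week 4, with Clopper-Pearson intervals, and names the test as Fisher's: "Exact Test will be used for computing p-value for treatment comparison between orvepitant (10 mg or 30 mg once daily") and placebo. Chi-square is allowed if Fisher cannot be computed. Footnote 5 defines response: "Total score increase of ≥5.0".

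The design makes these data paired:
- SAP 2.4: patients take orvepitant or placebo in Period A, "followed by the alternate treatment in Treatment Period B".
- SAP 7.1.2.11: "K-BILD will be completed by subjects at Visits 2, 4, 5 and 7", that is, before and at the end of both periods.
- SAP 5.1: "All analysis will be analysed by cohort such that there will be two placebo groups presented". SAP 7.1: "Statistical comparisons for the primary and secondary endpoints will be done separately for each cohort". Each placebo group therefore consists of the same patients as its orvepitant group.
- SAP 5.2.2: for secondary change endpoints, "the period-specific baseline will be used when available".

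The continuous analyses respect the pairing. The SAP 7.1 model contains period, and "Subject will be included as a random effect". The mean K-BILD change uses a similar model, and SAP 14.2 bases the sample size on a paired t-test. Neither document restricts the responder test to Period A or names a paired method for binary outcomes.

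**The concern.** Fisher's exact test and Pearson's chi-square treat the orvepitant and placebo columns as different people. With n patients contributing to both, the variance of the difference in proportions is

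Var = [p1(1-p1) + p2(1-p2) - 2φ√(p1(1-p1)p2(1-p2))] / n,

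where φ is the within-patient correlation of the two binary outcomes. An unpaired test drops the φ term. With equal response rates, the true variance is (1-φ) times what the test assumes. Positive φ makes the test too cautious and costs power. Sufficiently negative φ pushes its error rate above nominal.

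The usual defence, that ignoring pairing is merely conservative, cannot be taken for granted here. Response is a change from a period-specific baseline, so a patient's stable K-BILD level cancels out and with it the usual source of positive correlation. At stake are two unadjusted p-values on a listed secondary endpoint. The choice of test can also move a result across 0.05, so it should be settled before unblinding.

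**Working it through.** **1. The plan's own figure.** SAP 2.5.1 gives 37 evaluable patients per cohort for the primary endpoint (difference 1.5, SD of the paired difference 2.7, two-sided 0.05, 90% power). A paired t-test with noncentrality (1.5/2.7)√n gives 89.98% at n=36 and 90.8% at n=37, so 37 is reproduced and is a paired calculation. No power or size is stated for the responder test.

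**2. Same margins, different pairing.** Take 18/37 responders on orvepitant and 9/37 on placebo (illustrative counts). Fisher sees only these margins. Exact McNemar uses the discordant counts b (orvepitant only) and c (placebo only): p = 2·P(Bin(b+c, ½) ≤ min(b,c)).

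| Both | b | c | Neither | φ | Fisher p | McNemar p |
|---|---|---|---|---|---|---|
| 9 | 9 | 0 | 19 | 0.58 | 0.052 | 2×(½)^9 = 0.004 |
| 5 | 13 | 4 | 15 | 0.08 | 0.052 | 2×3214/131072 = 0.049 |
| 0 | 18 | 9 | 10 | -0.55 | 0.052 | 0.122 |

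Here φ = (both×neither - bc)/√(18×19×9×28); for the first row, 171/293.6 = 0.58. The outer rows are extremes. The middle row, close to independence, gives almost the same p-value by either test.

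**3. Size and power.** Assumptions, none of them in the documents: 37 complete pairs; 35% responders on both treatments for size; 50% versus 25% for power; the two responses generated by a bivariate normal with latent correlation r. All possible tables were enumerated exactly, with rejection at p ≤ 0.05.

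| r | Size: Fisher | Size: McNemar | Power: Fisher | Power: McNemar |
|---|---|---|---|---|
| -0.6 | 6.0% | 2.9% | 51% | 39% |
| -0.3 | 4.3% | 3.0% | 51% | 44% |
| -0.1 | 3.3% | 3.0% | 51% | 49% |
| 0 | 2.8% | 2.9% | 51% | 51% |
| 0.1 | 2.4% | 2.8% | 51% | 54% |
| 0.3 | 1.5% | 2.6% | 51% | 59% |
| 0.5 | 0.8% | 2.4% | 51% | 66% |

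Fisher's size passes 5% between r = -0.4 (4.9%) and r = -0.5 (5.4%).

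**4. What sign might r have?** The K-BILD visits fall at weeks 0, 4, 7 and 11. If all four scores are equally correlated, the two change scores have correlation 0. If the scores follow a weekly AR(1) process with parameter a, the correlation of the two changes is

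(2a^7 - a^3 - a^11) / [2(1 - a^4)] = -a^3(1 - a^4)/2.

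For a = 0.90: -0.729×0.3439/2 = -0.13. For a = 0.95 and 0.98 it is -0.08 and -0.04. The most negative value occurs at a^4 = 3/7 and equals -(3/7)^0.75×(4/7)/2 = -0.15. A positive r requires patients who respond, or fail to respond, consistently in both periods, whichever treatment they are on. The documents give no information on that.

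**5. Patients with one period only.** Protocol 7.1 plans about 88 patients, 44 per cohort. Suppose 37 have both periods and 44-37 = 7 have one (4 orvepitant, 3 placebo; assumed). In simulation, Fisher on all data has 60%, 61%, 61% and 62% power at r = -0.3, 0, 0.3 and 0.5. Complete-pair McNemar has 44%, 51%, 59% and 66%. Part of Fisher's rise from 51% is discreteness of the exact test rather than information.

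**The case against.** The strongest reply is that little practical harm follows. Under the simple correlation structures in step 4, r lies between -0.15 and 0. Across r = -0.13 to 0, Fisher's size is 2.8-3.5%, below nominal, and its power is 51% against 48-51% for exact McNemar. The larger power loss needs r of 0.3 to 0.5, and inflation needs r below about -0.4. The chi-square fallback is more exposed (size 6.9% at r = -0.3), but Fisher is always feasible for a 2×2 table of this size, so the fallback should never be used. Complete-pair tests can also do worse than Fisher when correlation is zero or negative, or when one-period patients are dropped. Finally, K-BILD change already has a proper crossover ANCOVA, and the responder test is an additional secondary analysis in a phase 2 trial.

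All of this stands, and it limits the severity and shapes the remedy. It does not rescue the test: its independence assumption is false by design, its behaviour depends on a quantity the documents leave unknown, and the SAP gives no reason for departing from the paired approach it uses elsewhere. One valid crossover use of Fisher's test, Mainland-Gart, compares preference between sequences. SAP 7.1.2.11 describes a comparison of response proportions between treatments instead.

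**Conclusion.** The point holds: the method is wrong as written, and minor in consequence. In each cohort an independent-groups test is applied to paired outcomes, and period is ignored. That follows from the text alone and needs no assumption.

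The size of the effect does depend on assumptions (37 pairs, the response rates in step 3, a latent normal model). Over r from -0.6 to 0.5, Fisher's true size ranges from 6.0% to 0.8% at a nominal 5%. Relative to exact McNemar, its power is 12 points higher at r = -0.6 (51% against 39%), equal at r = 0, and 15 points lower at r = 0.5 (51% against 66%). The direction cannot be settled from the documents, and near zero correlation the impact is small. Two p-values are affected. The primary endpoint, the sample size and the K-BILD mean-score analysis are not.

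**What to change.** Before unblinding, replace Fisher and chi-square in SAP 7.1.2.11 with one paired, period-adjusted method within each cohort. The most suitable is a logistic GEE with treatment and period as fixed terms and patient as the cluster. It keeps one-period patients, in line with SAP 5.3.1, and allows correlation of either sign, whereas a random intercept models only positive correlation. With about 37 to 44 patients per cohort, the SAP should also name the variance estimator.

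Report the paired risk difference with its 95% CI. One option is the within-patient difference averaged over the two sequences with a t interval; in simulation its size was 4.8-5.1% and its coverage 94.7-95.1% for r from -0.6 to 0.5, with or without a period shift of 0.5 latent SD. That version uses complete pairs only. A cluster-robust difference that keeps one-period patients, checked without a period term, held size at 5.0-5.3% over the same range. Mainland-Gart or exact or mid-p McNemar would be acceptable as simpler tests, at the price of dropping one-period patients. The per-treatment Clopper-Pearson intervals can stay.

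The cost is two or three SAP sentences and a few lines of code, with no new data. If correlation proves to be zero or negative, a paired test may have somewhat less power than Fisher would have shown.
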